# 8.7 Relationship to test vaccine (Did the test vaccine cause the adverse experience?):

The determination of the likelihood that the test vaccine caused the adverse experience will be provided by an investigator who is a qualified physician. The investigator's signed/dated initials and date on the source document or worksheet, that supports the causality noted on the AE form, ensures that a medically qualified assessment of causality was done. This initialed document must be retained for the required regulatory time frame. The criteria below are intended as reference guidelines to assist the investigator in assessing the likelihood of a relation the between the test vaccine and the adverse experience based upon the available information.

FACULTY OF TROPICAL MEDICINE MAHIDOL UNIVERSITY An adverse event's relationship to study medication assessment must be made by a medically qualified principal investigator or sub-investigator. The principle investigator or sub-investigator making relationship assessment must document this assessment in the subject's chart or file. The assessment of Causality is reported according to the investigator's best clinical judgment.

- "Related" should be selected if there is evidence of exposure to the test vaccine and the temporal sequence of the AE onset relative to administration of the test vaccine is reasonable. The AE is more likely explained by the test vaccine than by another cause. The AE shows a pattern consistent with previous knowledge of the test vaccine or test vaccine class. Or the AE could have been due to another equally likely cause.
- "Not related" should be selected if the subject did not receive the test vaccine OR temporal sequence of the AE onset relative to administration of the test vaccine is not reasonable OR there is another obvious cause of the AE. OR there is another more likely cause of the AE.
- "Not related" should be selected for subject's with accidental overdose without an associated AE.

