# 5.3.2 Blinding and Unblinding Procedures

The randomization will be conducted by an organization or individual not involved in day to day the conduct of the study. The investigator will assign the unblinded staff responsible for vaccine preparation, administration, handling and accountability and to ensure that blinding is protected throughout the study procedures and no other site personnel involved in the conduct of the study has access to the information. After assessment of eligibility of a new subject, the Subject Number will be assigned to each subject sequentially in the order they are enrolled. The unblinded staff will prepare and administer vaccine/comparator according to randomization list provided by BIOPHICS. The unblinded staff will be responsible to keep the randomization list in a safe, locked and secured place with no access by other site personnel until the database is locked.

The randomization lists will be provided to GPO for them to label the study vaccine and comparator syringes and then placed in a sealed envelope immediately afterward. It will be opened only after the clinical trial database is declared complete and locked. In the case of any unblinding, researchers must report this in writing to the overseeing ethics committee.

The vial labeling will be done at GPO before study vaccine and comparator are shipped. Study product injected into each participant will be recorded on the Case Report Form (CRF) using the exact allocation code for each product received by each participant.

The allocation codes link treatment identification with each participant identification number. These will be maintained in a secure location, by an individual not involved in the conduct of the study. If the investigator determines that it is necessary to unblind a participant, for example because a participant experiences an SAE possibly related to receipt of study treatment, then the treatment allocation to the participant will be communicated to the investigator.

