#### **Stopping rules:**

The occurrence of one or more of the following criteria will automatically pause or halt further vaccinations in the study:

- 1. One or more subjects experience a serious adverse event (SAE) that is suspected to be vaccine related.
- 2. One or more subjects experience a grade 4 injection site reaction (such as necrosis or sterile abscess at injection site requiring surgical intervention) that is suspected to be vaccine related.
- 3. Ten or more subjects experience a grade 3 or greater reactogenicity event following vaccination that is suspected to be vaccine related.
- 4. Five or more subjects experience the same grade 3 or more clinical abnormality following vaccination that is expected to be vaccine related

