# **11.4 Analysis of Safety Endpoints**

The safety profile of the GPO Tri Fluvac will be evaluated by the number and proportion of participants experiencing AEs by severity and relatedness to vaccination of the following five categories for all participants:

- A. Solicited local adverse events, including redness / erythema, swelling / induration, pain within 30 minutes of vaccination and over a 3-day period (Day 0-3) post-vaccination.
- B. Solicited systemic adverse events, including fever, fatigue, malaise, muscle aches, joint aches, chills, nausea, and headache within 30 minutes of vaccination and over a 3-day period (Days 0-3) post-vaccination.
- C. Unsolicited AEs occurring within 90 days post vaccination.
- D. SAEs occurring during the entire study period (Days 0-90).

Occurrences of all events will be reported and summarized according to event severity, as "any local AE", or "any systemic AE", and by relationship to administration of study product, as deemed by a blinded study clinician. Percentage of participants experiencing each reaction or event, or at least one reaction or event will be calculated along with two-sided exact 95% CIs. No statistical testing will be performed for unsolicited AEs; including SAEs. The percentage of participants with solicited AE and SAEs will be compared between vaccine and comparator groups and a two-sided p-value of 0.05 will be considered statistically significant.

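### Section 8.7 lets non-receipt of the test vaccine decide causality, a criterion that a blinded rater cannot check and that treats the two arms differently once an individual code is broken

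*Protocol*

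**What the plan says.** Section 8.7 of the protocol asks whether the test vaccine caused the event and gives two ratings.

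- *Related* "should be selected if there is evidence of exposure to the test vaccine and the temporal sequence of the AE onset" relative to vaccination is reasonable. Further considerations are a more likely explanation by the vaccine and a pattern known for it or its class.
- *Not related* "should be selected if the subject did not receive the test vaccine OR temporal" sequence is unreasonable, or there is an obvious or a more likely other cause.

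The section qualifies its own list: "The criteria below are intended as reference guidelines to assist the investigator in assessing the likelihood". It adds: "The assessment of Causality is reported according to the investigator's best clinical judgment". It also describes the assessment once as one of relationship to study medication.

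The analysis text puts a different question. Section 11.4 summarises events "by relationship to administration of study product, as deemed by a blinded study clinician"; the protocol summary and the SAP synopsis say the same. SAP tables TREF 2.1 and 2.4 have related-event columns for both arms.

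Section 4.1 keeps investigators blinded until the database is locked. Section 5.3.2 allows an exception if the investigator finds unblinding necessary, with a possibly related SAE as the example: "then the treatment allocation to the participant will be communicated to the investigator".

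**The concern.** A causality rating that feeds a two-arm safety table should ask the same question of every participant and should not depend on which product was given. Section 8.7 departs from this in two ways. It names one product as the possible cause, and it makes not having received that product sufficient for *Not related*.

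That criterion can make sense against placebo. Here section 4.5 describes the comparator as a licensed split-virion vaccine with 15 µg of haemagglutinin of each of the same three strains, so reactions of the same kind can be expected from both products.

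At stake is the consistency of the related-AE and related-SAE rows. Relatedness also enters the expedited review list (9.2), the follow-up of ongoing related SAEs after study end (8.8) and the stopping rules (9.3), where one case is enough for the first: "One or more subjects experience a serious adverse event (SAE) that is suspected to be vaccine related".

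**Working it through.** No figure in the plan depends on this point, so the check sets the passages side by side.

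**1. What the term means.** *Test vaccine* is not defined. Where the protocol means both arms it names vaccine and comparator together (8.3) or says study product (8.8, 11.4). There are two readings.
- Tri Fluvac only. All 315 planned comparator recipients then meet the non-receipt criterion, whatever the event.
- Either injection. Nobody under assessment then meets it: the safety population (11.3.1) consists of vaccinated subjects, and unsolicited AEs (8.3) begin after the injection.

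So the criterion either depends on allocation or does nothing. Neither reading gives a reason to keep it.

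**2. What a blinded rater can apply.**
- Non-receipt of the test vaccine, read as Tri Fluvac: no.
- Exposure to the test vaccine, on the same reading: no.
- Timing of onset after the injection: yes.
- Obvious, more likely or equally likely other cause: yes.
- Pattern known for the vaccine class: yes, since both products are inactivated split-virion influenza vaccines.

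Causality can therefore be judged blind, but not with the list exactly as written.

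**3. Which events are exposed.** Section 8.2 requires no causality assessment for solicited AEs with onset in the solicitation period. That leaves unsolicited AEs and SAEs.

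**4. When allocation is known.** Before lock it is known to an investigator only after an individual code break (5.3.1, 5.3.2). No section plans recoding after lock. Equally, no section says that the rating must be recorded before a code break or left unchanged after it.

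**5. The remaining asymmetry.** Take two identical SAEs, each with plausible timing and no better explanation, and break both codes. Read literally, the comparator case becomes *Not related* through the first criterion, while the Tri Fluvac case can be *Related*. The direction is against Tri Fluvac.

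**6. Size.** The documents give no expected number of code breaks, so call it *k*. If breaks occur independently of arm (an assumption), the expected number in the comparator arm is k × 315/945 = k/3. For k = 3 that is one participant, and the rating changes only if it is revised afterwards and the wording is taken literally.

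**7. The tabulated variable.** Section 8.7 has two categories. The notes to TREF 2.1 and 2.4 build the suspected-related group from three grades: probably not, probably and definitely related. Two categories cannot supply these grades, and the lowest of the three would more naturally fall on the unrelated side.

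**The case against.** The strongest reply is that this is loose terminology which the plan already contains. The list is guidance subject to clinical judgment. The analysis sections name the study product and a blinded assessor. Unblinded staff take no part in safety evaluation (4.6.3). Suspicion also comes before unblinding: in 5.3.2 a possibly related SAE is what prompts the code break. In Appendix B the suspected causal relationship is in the first notification (6.1.1) and the Safety Medical Team assesses causality (6.3.1) before it decides on unblinding (6.5.3). All of this stands, and it confines the problem to revision after a code break. It does not remove it: nothing fixes the earlier rating, and raters who follow the wording will differ from raters who override it.

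Three stronger inferences are tempting, and the documents support none of them.

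- *The related count in the comparator arm would be forced to 0/315.* This needs allocation known for every comparator recipient when events are rated. For scale only, at an assumed equal true rate of 2%, 13/630 v 6/315 would become 13/630 v 0/315 (Fisher p = 0.006). At 1%, 6 v 3 would become 6 v 0 (p = 0.19). Section 2.4 reports two suspected-related events among 200 vaccinees in the earlier trial, 2/200 = 1%. No planned step produces such a recoding.
- *A comparator reaction could never trigger a pause.* The stopping rules speak of vaccine-related events and 9.2 of the study agent. A blinded investigator who suspects the injection can trigger either in either arm.
- *The relatedness columns cannot be compared between arms.* Ratings made blind on timing, other causes and class pattern are comparable. TREF 2.1 and 2.4 also carry no p-value row, so no test in those tables is distorted.

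**Conclusion.** The point holds in a limited form. Section 8.7 contains an allocation-dependent criterion that the required blinded rater cannot check and that conflicts with the two-arm study-product assessment in 11.4 and the SAP. This rests on reading *test vaccine* as Tri Fluvac, which is the plain reading but not the only one.

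The practical bias is confined to unsolicited AEs and SAEs of individually unblinded participants, about a third of whom would be comparator recipients under the assumption in the check. It would work against Tri Fluvac. The affected number is likely to be small but cannot be computed from the documents. The mismatch between the causality categories of 8.7 and those of the SAP does not depend on any of this and needs resolving in its own right.

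**What to change.** 1. In section 8.7 and the AE form instructions, define the object of assessment as the study product received, Tri Fluvac or comparator, with allocation unknown, and use that term throughout.
2. Delete the non-receipt criterion.
3. State that the rating tabulated in TREF 2.1 and 2.4 is the one recorded before any code break and is not changed because of allocation.
4. Reconcile the two categories of 8.7 with the SAP's three-grade suspected-related grouping, so that the variable tabulated is the one collected.

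This is a wording amendment to the protocol, the AE form instructions and the SAP table notes. If the finer grades are kept, the AE form must collect them. No extra participants, visits or samples are needed, and no clinical rule changes.

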# 8.8 Follow up of AE

All reported AEs should be followed until resolution or stabilization, or until the participant's participation in the study ends. Participants who have an ongoing study product-related SAE at study completion or at discontinuation from the study will be followed with by the PI or his designee until the event is resolved or determined to be irreversible, chronic, or stable by the PI.

# 8.9 General Guidelines for Recording AEs

To improve the quality and precision of acquired AE data, the Principal Investigator or designees should observe the following guidelines:

- Whenever possible, use recognized medical terms when recording AEs on the AE CRF. Do not use colloquialisms and/or abbreviations.
- If known, record the diagnosis (i.e., disease or syndrome) rather than component signs, symptoms and laboratory values on the AE CRF (e.g., record congestive heart failure rather than dyspnea, rales, and cyanosis). However, signs and symptoms that are considered unrelated to an encountered syndrome or disease should be recorded as individual AEs on the CRF (e.g., if congestive heart failure and severe headache are observed at the same time, each event should be recorded as an individual AE).
- AEs occurring secondary to other events (e.g., sequelae) should be identified by the primary cause. A "primary" AE, if clearly identifiable, generally represents the most accurate clinical term to record on the AE CRF. If a primary SAE is recorded on an SAE CRF, events occurring secondary to the primary event should be described in the narrative description of the case.

For example:

Orthostatic Fainting and Hypotension fall to floor The primary AE is orthostatic hypotension. Head trauma

Protocol: GPO Tri Fluvac Vaccine Phase II/III\_ Version 3.1 dated 13 Mar 2017

- Death is an outcome of an event. The event that resulted in the death should be recorded and reported on the SAE CRF.
- For hospitalizations for surgical or diagnostic procedures, the illness leading to the surgical or diagnostic procedure should be recorded as the SAE, not the procedure itself. The procedure should be captured in the case narrative as part of the action taken in response to the illness.
- Pregnancies are not considered AEs. They will be recorded on a separate Pregnancy CRF. Pregnancy outcomes that include stillbirth and any congenital anomalies must be reported as SAEs.

#### 8.10 Unexpected Allergic Reactions

Immediate Reactions (within 30 minutes)

All participants will be observed for 30 minutes after administration of study product, with appropriate medical treatment readily available in case of an anaphylactic reaction following the administration of study product. Immediate reactions will be assessed by a study physician or appropriately trained medical staff. All reactions that occur during this time will be recorded on the CRF. Any immediate reaction that meets the criteria for an SAE must also be documented on an SAE form.

Emergency medicines will be available at the study clinic to be ready to give first aid if any adverse reactions or events should occur among any participant participating in this research.

## 8.11 Clinical evaluations

#### 8.11.1 Vital Signs

The vital signs in this study include temperature in degrees Celsius (recorded to the nearest 0.1 degree) by oral thermometer; blood pressure in millimetres of mercury; and heart rates in beats per minute, measured by automated device or manually.

# 8.11.2 Medical History

At enrollment, medical histories must be thoroughly reviewed with the participant. The following medical conditions, in particular, will be assessed:

- Current or recent (within two weeks of enrollment) acute illness with or without fever.
- Recent vaccination history.
- Recent receipt of immune globulin or other blood products, or injected or oral corticosteroids or other immune modulator therapy within six weeks before enrollment.
- Hypersensitivity of any kind, but particularly to vaccines and egg proteins.
- Clinically relevant history of renal, gastrointestinal, hepatic, cardiovascular, hematological, dermatological, endocrine, neurological, or immunological diseases.
- Seizures, including history of febrile seizures, or any other neurologic disorder.
- Known or suspected immunologic impairment of any kind.
- Known HIV infection.
- Known active tuberculosis disease.
- Alcohol or drug abuse.
- Concomitant medications that are ongoing (including trade name, dosing, date).

ETHICS CON Indications, start

APPROVE

MAHIDOL UNIVERSITY

CAL MEDICINE

• For women, pregnancy, menstrual, and contraceptive history and/or history of surgical sterility.

# 8.11.3 Physical Examination

# General Physical Examinations

Qualified study clinicians will conduct a physical examination of all participants at S1. This physical examination will include the following:

- Recording of general appearance
- Physical examination of all organ systems. This includes the following:
  - Brief neurologic examination
  - Chest auscultation
  - Examination of lymph nodes (axillary and cervical)
  - Heart auscultation
  - Abdomen palpation (to check for liver size)
  - Measurement of the following vital signs:
    - body temperature
    - blood pressure
    - pulse/heart rate

\* Elevated blood pressure not greater than Grade 1 (Systolic  $\geq$ 140-159 or diastolic >90-99) will not be considered to be exclusionary at screening unless judged to be clinically significant by the PI or clinician designee.

# Targeted Physical Examination

The Targeted Physical examination (PE) focuses on symptoms reported by the participant and the presence or absence of local and systemic reactogenicity. If no symptoms are reported by the participant, the Targeted PE does not need to be performed.

# 8.11.4 Injection Site Examination

Assessment of local Injection site reaction 30 minutes after vaccination will be done by trained

study personnel and graded for severity according to the toxicity grading table in Appendix A.

- Erythema /redness will be examined under proper lighting conditions and measured with a ruler if present.
- Swelling/inducation will be examined by palpation and visual inspection under proper lighting conditions. The examiner may temporarily mark skin at margins of visible swelling/inducation, then measure with a ruler the maximum diameter.
- Pain will be assessed by inquiring as to whether there is significant discomfort at rest.
- Limitation of arm movement of the injection site causes discomfort, impacts limb movement or daily activity.

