# **Primary Safety Endpoints:**

The number and proportion of participants reporting the following events will be assessed:

- Solicited local adverse events, including redness / erythema, swelling / induration, pain, and limitation of arm movement within 30 minutes of vaccination and over the 3-day period post-vaccination (Days 0-3).
- Solicited systemic adverse events, including fever, fatigue/malaise, muscle aches, joint aches, chills, nausea, and headache within 30 minutes of vaccination and over the 3-day period post-vaccination (Day 0-3).
- Unsolicited Adverse Events (AEs) occurring within 90 days post-vaccination.
- Serious Adverse Events (SAE) occurring during the entire study period (Days 0-90).

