# 7.4 Follow-up visits

# 7.4.1 Day 7(-3, +7 days) after Injection: Return the diary card

Subjects will return to the clinic on day 7 to return the diary card and report any adverse events. Subjects will be asked to report any adverse events that occur during the first seven days after immunization. Concomitant medication information will be collected.

At this visit;

- 1. Study staff will confirm participant identity.
- 2. Study staff will review the participant diary card and interim history with the participant and inquire about any new medical events since medical histories were last updated. Any AEs that have occurred and meeting reporting intensity will be recorded in the appropriate section(s) of the CRF. Diary card information will be entered into the CRF.
- 3. The participant will have temperature, pulse rate, and blood pressure recorded. A study clinician will perform a targeted (symptom based) physical examination and record the information on the CRF. Results will be reviewed by study staff and with the participant.
- 4. The participant will be instructed to inform the investigator as soon as possible if he/she experiences an AE requiring medical care and to seek medical care as appropriate. If the participant visits a health care provider, the participant should be sure to inform the health care provider of participation in this study and give the health care provider the contact information for the investigator.
- 5. There are no scheduled visits at week 2 after vaccination. Participants may be asked to come to the study clinic if the investigator follows up on any clinical issue. The participant will inform the study clinic of any medical events and seek medical care as needed. The participant will be instructed to give any health care provide they see the contact information for the investigator. FACULTY OF TROPICAL MEDICINE วิตยาลัยม

MAHIDOL UNIVERSITY

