# 8. SAFETY AND LABORATORY EVALUATIONS

## 8.1 Safety Evaluations

All adverse experiences will be collected after the immunization throughout the period of the study. Such events will be recorded at each examination on the Adverse Experience Case Report Forms/Worksheets. Serious adverse experiences will also be collected and reported.

- Immediate reactions occurring within 30 minutes of vaccine administration
- Commonly occurring adverse events associated with vaccination, i.e., solicited adverse symptoms recorded during days 1-3.

• All other adverse events (including unsolicited events) occurring throughout the period of the study

An adverse experience is defined as any unfavorable and unintended change in the structure, function, or chemistry of the body temporally associated with the use of vaccine, whether or not considered related to the use of the product. Any worsening (i.e. any clinically significant adverse change in frequency and/or intensity) of a preexisting condition, which is temporally associated with the use of the vaccine, is also an adverse experience. The occurrence of an AE might come to the attention of study personnel during study visits and interviews of a study participant presenting for medical care. Information to be collected on AEs includes event description, time of onset, clinician's assessment of severity, relationship to study product, and time of resolution/stabilization of the event. AE assessment should be made only by those with the training and authority to make a diagnosis. Any medical condition that was present at the time that the participant was enrolled should not be reported as an AE, but should be reported as a pre-existing condition on the Medical VED History Form. However, if this condition occurs with greater frequency or severity during the study, it should be recorded as an AE

Protocol: GPO Tri Fluvac Vaccine Phase II/III\_ Version 3.1 dated 13 Mar 2017

MAHIDOL UNIVERSITY

ไตยาลัยม

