## 8.2 Solicited Local and Systemic Adverse Events

Solicited adverse events are pre-specified local and systemic adverse events that are common or known to be associated with vaccination and that are actively monitored as indicators of vaccine reactogenicity. Investigators will not be required to assess causality of solicited adverse events if the onset is during the solicitation periods. If a solicited adverse event progresses beyond the solicited period, it will continue to be reported as a solicited adverse event. If the solicited adverse event occurs after the solicitation period, it will be reported as unsolicited AEs.

For this trial, solicited local and systemic AEs will be assessed by study staff 30 minutes after vaccination then daily for three days by the participants. Participants will be provided with a thermometer, ruler, and diary card to record the presence or absence of solicited AEs, severity of the solicited AE, and use of concomitant medication. The severity of the solicited local and systemic adverse events will be graded using the Toxicity Table for Grading Adverse Events (Appendix A). The specific solicited local and systemic adverse events that will be reported for this trial are:

Solicited local adverse event (at site of injection):

- Erythema/redness—based on size in cm.
- Swelling/induration (hardness at site of injection)—based on size in cm.
- Pain (pain with or without touching the injection site).
- Limitation of arm movement

Systemic Reactions:

- Fever—taken orally by thermometer
- Fatigue/malaise
- Generalized muscle aches
- Joint aches
- Chills
- Nausea
- Headache

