Vomiting	Transient or intermittent AND No or minimal interference with oral intake	Frequent episodes with no or mild dehydration	Persistent vomiting resulting in orthostatic hypotension OR Aggressive rehydration indicated (e.g., IV fluids)	Life-threatening consequences (e.g., hypotensive shock
Headache	Symptoms causing no or minimal interference with usual social & functional activities	Symptoms causing greater than minimal interference with usual social & functional activities	Symptoms causing inability to perform usual social & functional activities	Symptoms causing inability to perform basic self-care functions OR Hospitalization indicated OR Headache with significant impairment of alertness or other neurologic function
INJECTION SITE	REACTIONS			
Injection Site Pain or Tenderness Report only one	Pain or tenderness causing no or minimal limitation of use of limb	Pain or tenderness causing greater than minimal limitation of use of limb	Pain or tenderness causing inability to perform usual social & functional activities	Pain or tenderness causing inability to perform basic self- care function OR Hospitalization indicated
Injection Site Erythema or Redness Report only one > 15 years of age	2.5 to < 5 cm in diameter OR 6.25 to < 25 cm2 surface area AND Symptoms causing no or minimal interference with usual social & functional activities	$\geq$ 5 to < 10 cm in diameter OR $\geq$ 25 to < 100 cm2 surface area OR Symptoms causing greater than minimal interference with usual social & functional activities	$\geq$ 10 cm in diameter OR $\geq$ 100 cm2 surface area OR Ulceration OR Secondary infection OR Phlebitis OR Sterile abscess OR Drainage OR Symptoms causing inability to perform usual social & functional activities	Potentially life- threatening consequences (e.g., abscess, exfoliative dermatitis, necrosis involving dermis or deeper tissue)

Protocol: GPO Tri Fluvac Vaccine Phase II/III\_ Version 3.1 dated 13 Mar 2017

MUINE MAHIDOL UNIVERSITY

E.

PARAMETER GRADE 1 MILD		GRADE 2 MODERATE	GRADE 3 SEVERE	GRADE 4 POTENTIALLY LIFE-
Injection Site Induration or Swelling Report only one > 15 years of age	Same as forSame as forInjection SiteImageErythema orImageRedness, $> 15$ ImageyearsImage	Same as for Injection Site Erythema or Redness, > 15 years of age	Same as for Injection Site Erythema or Redness, > 15 years of Age	Same as for Injection Site Erythema or Redness, > 15 years of age

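### The 30-minute pain question is narrower than the pain endpoint, and the Day 7 recording rule uses an undefined intensity threshold; each may under-record low-grade events

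*Protocol*

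**What the plan says.** **Pain.** The primary safety endpoint in Protocol section 3 counts "pain, and limitation of arm movement within 30 minutes of vaccination and over the 3-day period post-vaccination (Days 0-3"), with no intensity threshold. Section 8.2 names the assessors: "solicited local and systemic AEs will be assessed by study staff 30 minutes after vaccination then daily for three days by the participants". It defines the event as "Pain (pain with or without touching the injection site"). Section 8.11.4 covers the 30-minute examination. Reactions are to be assessed by "study personnel and graded for severity according to the toxicity grading table in Appendix A", but the question for pain is "Pain will be assessed by inquiring as to whether there is significant discomfort at rest". Grade 1 pain in Appendix A is "Pain or tenderness causing no or minimal limitation of use of limb".

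**Adverse events at Day 7.** Section 7.4.1 says: "Any AEs that have occurred and meeting reporting intensity will be recorded in the appropriate section(s) of the CRF". Section 8.1 says: "All adverse experiences will be collected after the immunization throughout the period of the study". Section 8.5 sets the reporting period for unsolicited events as Day 0 to Day 90, without an intensity limit.

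**The concern.** Two instructions to site staff do not match the safety endpoints they serve.

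At 30 minutes, a participant with mild discomfort at rest, or with pain only when the site is pressed, meets the 8.2 definition but could truthfully answer no to the 8.11.4 question. The SAP reports this time point separately. TREF 3.6 compares the arms on pain at 30 minutes with a p-value, and TREF 3.8 has a row for pain present only then. Pain also weighs heavily in the local summaries: TREF 3.5 leaves out erythema and induration, and TREF 3.7 grades only pain and limitation of arm movement.

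At Day 7, the first visit after vaccination, staff are given an intensity condition with no stated cut-off. One reader could record everything and another could leave out mild events. The number and percentage of participants with unsolicited events is part of the primary safety endpoint, so the recording rule should not be open to interpretation.

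**Working it through.** No figure in the documents is at issue, so the check is a comparison of passages, with a little algebra on how far the pain problem can reach.

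**1. Pain definition against pain question**

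| Source | Pain on touch or tenderness | Mild pain at rest |
|---|---|---|
| 8.2 definition | included | included |
| Appendix A, Grade 1 | included | included |
| 8.10, immediate reactions | all reactions recorded | all reactions recorded |
| 8.11.4, pain question | not asked | not asked unless significant |

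Section 8.11.4 therefore conflicts with 8.2 and 8.10. It also conflicts with itself: it calls for Appendix A grading but does not ask about the tenderness that Grade 1 contains.

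**2. Which pain outputs are exposed**

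- TREF 3.6, 30-minute column: directly. If the narrow question detects a fraction c of endpoint pain in each arm, the recorded rates are c·p₁ and c·p₂. Their difference is c·(p₁ − p₂) and their ratio is unchanged. The value of c is unknown, and taking it as equal in both arms is an assumption, supported by blinded assessment.
- TREF 3.8, 30-minutes-only row: directly, because only the clinic check feeds it.
- Any-day pain: indirectly. Let p be the true any-day rate and s the share of those participants whose pain occurs only at 30 minutes. Then recorded rate = p × [1 − s × (1 − c)].

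With s = 0 the bracket equals 1, so the any-day rate does not move whatever c is. To show how the formula behaves, take p = 32.5%, the vaccine-arm pain rate from the earlier Tri Fluvac trial (Protocol 2.4). Both s and c are assumed:

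| s | c = 0.25 | c = 0.75 |
|---|---|---|
| 0 | 32.5% | 32.5% |
| 0.10 | 0.325 × 0.925 = 30.1% | 0.325 × 0.975 = 31.7% |
| 0.25 | 0.325 × 0.8125 = 26.4% | 0.325 × 0.9375 = 30.5% |

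This is a range over assumptions, not an estimate of loss. The documents give neither s nor c, and Protocol 2.4 does not say when that pain was assessed.

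**3. Whether the diary covers the gap**

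Section 7.3 starts the diary on the day after injection. Section 4.1 and Table 2 say Day 0-3. TREF 3.6 has columns for 30 minutes and Days 1, 2 and 3 only. The clinic check is thus the only Day 0 pain measure with its own column in that table.

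**4. Day 7 rule against the all-event rule**

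- Sections 8.1 and 8.5 require all adverse events, Day 0 to Day 90.
- Section 8.6 defines a mild Grade 1, and SAP TREF 2.2 has a row for mild events.
- Section 7.4.1 first asks participants for any adverse events, then limits recording by an intensity that no section defines.
- Sections 7.4.2 and 7.4.4 carry no such limit, but they ask about events since the last visit, so an event left out at Day 7 may not be asked about again.
- The same item of 7.4.1 enters diary information in the CRF without a filter, so solicited events from the diary are outside the problem. Under 8.3, a solicited-type symptom that starts after three days is unsolicited and falls within it.

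**The case against.** The strongest reply is that other text already secures full recording. Section 8.10 has all reactions within 30 minutes recorded (its heading concerns allergic reactions, but the sentence is not limited to them). Section 4.6.3 has staff observe participants and ask about their well-being. Section 8.11.4 points to Appendix A and lists limitation of arm movement, with its discomfort, as a separate item. TREF 3.5 and 3.7 take the maximum grade on any day, so pain that lasts into or begins on Days 1-3 is still counted. The staff worksheet and diary card are not in the documents, so the question actually put to participants is unknown.

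Most of this stands, and it limits the point to a conflict of instructions. It does not remove the conflict: staff who follow the one sentence written specifically for pain would not ask about touch, and they cannot grade what they have not elicited.

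A reader might infer that pain and mild adverse events are in fact undercounted. The documents do not support that. For pain, they show a risk confined to the 30-minute assessment. For Day 7, an undefined threshold cannot be shown to exclude Grade 1, and 8.1 and 8.5 point the other way. A reader might also infer a bias favouring one vaccine. Both arms get the same question from blinded assessors, and nothing in the text suggests a differential effect. The earlier trial's 32.5% against 19% is a placebo contrast at an unstated time, so it cannot size a 30-minute difference between two active vaccines.

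**Conclusion.** The point holds as two internal inconsistencies in how safety is measured.

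First, the 30-minute pain question in 8.11.4 is narrower than 8.2 and Appendix A Grade 1 and conflicts with 8.10. Taken literally, it may under-record pain at 30 minutes. The effect falls directly on one column of TREF 3.6 and one row of TREF 3.8. It reaches the any-day pain rate only through participants whose pain occurs solely at 30 minutes.

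Second, the Day 7 intensity condition in 7.4.1 is undefined and conflicts with 8.1 and 8.5. It could under-record low-grade unsolicited events; diary-recorded solicited events are not affected.

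The size of either loss cannot be derived from the documents. The conclusion assumes that staff follow 8.11.4 and 7.4.1 as worded and that no worksheet overrides them. The wording should be corrected because it bears on a primary safety endpoint and is cheap to change. It does not by itself undermine the between-arm safety comparison.

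**What to change.** - **8.11.4:** replace the pain sentence with a question about any pain at the injection site, whether or not the site is touched, graded by Appendix A. This brings the staff question into line with 8.2.
- **7.4.1:** delete the words that impose the intensity condition (and meeting reporting intensity), so that Day 7 recording follows 8.1 and 8.5.

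The cost is two wording edits, an update to the source worksheet and a few more mild events recorded. The registry entry reproduced with the protocol lists the study as completed, so the study report should also state which pain question was asked at 30 minutes and whether any intensity threshold was applied at Day 7.
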